Tamoxifen	20mg Tablets	Oral	daily continuous All cycles	3 weeks (21 days)
Vorinostat	400mg	Oral	Days 5/7 All cycles	
Pembrolizumab	200mg	Intravenous	Day 1, week 1 Cycles 2+	

Arm C (Figure 1)

Study Drug	Dose	Route	Schedule	Cycle Length
Vorinostat	400 mg	Oral	Days 5/7 All cycles	3 weeks (21 days)
Pembrolizumab	200 mg	Intravenous	Day 1, week 1 Cycles 1+	

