5.2 Monitoring and Toxicity Management

Each patient receiving pembrolizumab in combination with Tamoxifen and Vorinostat will be evaluable for safety. The safety parameters include all laboratory tests and hematological abnormalities, physical findings, and spontaneous reports of adverse events reported to the investigator by patients.

Each patient will be assessed periodically for the development of any toxicity as outlined in [Section 6 Study Procedures and Observations](#). Toxicity will be assessed according to the NCI [CTCAE v4.0](#). Dose adjustments will be made according to the system showing the greatest degree of toxicity.

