Pembrolizumab Arm A)	200 mg q every three weeks start on day 1 of cycle 1							
Pembrolizumab Arm B)	200 mg q every three weeks start on day 1 of cycle 2							

a) All screening procedures must be performed within 28 days unless otherwise indicated. Pre-study tests, History and Physical may be used for Day 1 tests if within 2 weeks

- b) Toxicity assessment must be performed until all treatment-related toxicities have been resolved or decreased to grade 1. Adverse events must be recorded up to 30 days after termination on study
- c) Every month for the first 6 cycles, then at least every 3 cycles thereafter, more frequently if clinically indicated
- d) For women of childbearing potential, performed within 7 days of starting treatment. Pregnancy test will be repeated if clinically indicated.
- e) Staging studies within 30 days prior to day of start, restaging after cycle 3 (week 9), 6 (week 18), then 9, 12, then every 6 cycles if clinically indicated. Partial and complete responses must be confirmed at least one month apart from the first documentation of objective response. Scans may be performed more frequently if clinically indicated.
- f) Pre-study within 14 days, and end of cycle 3 (preferably day 17-19) prior to cycle 4 day 1 pembrolizumab infusion.
- g) Cycle delays up to 5 days for non-medical reason (e.g. holidays) are acceptable without notification of regulatory agencies.
- h) On day 10-12 pre-dose.
- i) Sodium, Potassium, Chloride, blood urea nitrogen, Creatinine, Non-fasting glucose, Calcium, Magnesium, Phosphorus, ALT, AST, Alkaline Phosphatase, Albumin, Total Bilirubin, Total Protein
- j) Therapy delay for palliative radiation should be based on discussion with the study sponsor and the treating physician, every effort should be made not to hold therapy, patients where vorinostat is being held for more than 4 weeks may stay on study if there is felt to be a benefit

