7.6 Evaluation of an Adverse Event

All grade 3 and above adverse events will be entered into OnCore®, whether or not the event is believed to be associated with use of the study drug. Data about these events and their severity will be recorded using the NCI CTCAE v4.0.

The Investigator will assign attribution of the possible association of the event with use of the investigational drug, and this information will be entered into OnCore® using the classification system listed below:

Relationship	Attribution	Description
Unrelated to investigational drug/intervention	Unrelated	The AE is clearly NOT related to the intervention
	Unlikely	The AE is doubtfully related to the intervention
Related to investigational drug/intervention	Possible	The AE may be related to the intervention
	Probable	The AE is likely related to the intervention
	Definite	The AE is clearly related to the intervention

Signs or symptoms reported as adverse events will be graded and recorded by the Investigator according to the CTCAE. When specific adverse events are not listed in the CTCAE they will be graded by the Investigator as none, mild, moderate or severe according to the following grades and definitions:

- Grade 0 No AE (or within normal limits)
- Grade 1 Mild; asymptomatic or mild symptoms; clinical or diagnostic observations only; intervention not indicated
- Grade 2 Moderate; minimal, local, or noninvasive intervention (e.g., packing, cautery) indicated; limiting age-appropriate instrumental activities of daily living (ADL)
- Grade 3: Severe or medically significant but not immediately life-threatening; hospitalization or prolongation of hospitalization indicated; disabling; limiting self-care ADL
- Grade 4: Life-threatening consequences; urgent intervention indicated
- Grade 5: Death related to AE

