7.8 Adverse Events Reporting

All adverse events, whether or not unexpected, and whether or not considered to be associated with the use of the study drug, will be entered into OnCore®, as noted above.

The Investigator will assess all adverse events and determine reportability requirements to the UCSF Data and Safety Monitoring Committee (DSMC) and UCSF’s Institutional Review Board, the Committee on Human Research (CHR); and, when the study is conducted under an Investigational New Drug Application (IND), to the Food and Drug Administration (FDA) if it meets the FDA reporting criteria.

All adverse events entered into OnCore® will be reviewed by the Helen Diller Family Comprehensive Cancer Center Site Committee on a weekly basis. The Site Committee will review and discuss at each weekly meeting the selected toxicity, the toxicity grade, and the attribution of relationship of the adverse event to the administration of the study drug(s).

All grade(s) 3-5 adverse events entered into OnCore® will be reviewed on a monthly basis at the Site Committee meetings. The Site Committee will review and discuss the selected toxicity, the toxicity grade, and the attribution of relationship of the adverse event to the administration of the study drug(s).

In addition, all suspected adverse reactions considered “serious” entered into OnCore®, will be reviewed and monitored by the Data and Safety Monitoring Committee on an ongoing basis and discussed at DSMC meetings, which take place every six weeks.

For a detailed description of the Data and Safety Monitoring Plan for a Multicenter Phase 2 or 3 Institutional Study at the Helen Diller Comprehensive Cancer Center please refer Appendix 4 Multicenter Institutional Studies.\

7.8.1 Definition of an Overdose for This Protocol and Reporting of Overdose to the study PI and Merck.

For purposes of this trial, an overdose will be defined as any dose exceeding the prescribed dose for pembrolizumab by 20% over the prescribed dose. No specific information is available on the treatment of overdose of pembrolizumab. In the event of overdose, the subject should be observed closely for signs of toxicity. Appropriate supportive treatment should be provided if clinically indicated.

If an adverse event(s) is associated with (“results from”) the overdose of a Merck product, the adverse event(s) is reported as a serious adverse event, even if no other seriousness criteria are met.

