In addition to the interim analysis for efficacy that is built into the Simon 2-stage design (see above), in each arm we will evaluate the need for dose modification after 6 patients have been enrolled. If 2 or more patients have a grade 3 non-hematologic toxicity that is clearly related to pembrolizumab, this agent will be reduced to 75%. Dose modification of vorinostat should be undertaken as per dose modification guidelines, a prior study with vorinostat and tamoxifen suggest that there is a high interpatient variability and tolerance and vorinostat will be adjusted per dose modification guidelines individually.

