8.3 Analyses Plans

8.3.1 Analysis Populations

We will conduct an intention-to-treat analysis of efficacy. All patients who were randomized will be evaluated.

For evaluation of safety, we will restrict the arm-specific samples to all patients who have received at least one dose of investigational therapy.

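### The six-patient pembrolizumab toxicity look requires no pembrolizumab exposure or follow-up and, read literally, counts grade 3 but not grade 4–5 events; a minor wording repair

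*Combined protocol and SAP*

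**What the plan says.** Section 8.2 (Interim Analyses) adds a safety check to the Simon design: "in each arm we will evaluate the need for dose modification after 6 patients have been enrolled". The trigger reads: "If 2 or more patients have a grade 3 non-hematologic toxicity that is clearly related to pembrolizumab". The action is to lower pembrolizumab to 75%. The section states no required pembrolizumab dose, observation period, repeat look or accrual pause.

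One randomised ER+ arm starts pembrolizumab a cycle late. Table 5.1 gives its schedule as "Day 1, week 1 Cycles 2" onward, and the study calendar (Table 6) as "200 mg q every three weeks start on day 1 of cycle 2". These tables call it Arm B, while the synopsis and section 6.1 attach the late start to Arm A. On either label, one arm starts 21 days after the other.

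The nearest rules on exposure are these:

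- Section 5.2: "Each patient receiving pembrolizumab in combination with Tamoxifen and Vorinostat will be evaluable for safety".
- Section 7.1.2 makes patients evaluable for toxicity from their first study treatment.
- Section 8.3.1, for the safety analysis: "we will restrict the arm-specific samples to all patients who have received at least one dose of investigational therapy".
- A footnote to the neutropenia table in section 5.1.1.1 replaces patients whose dosing is delayed by more than 3 weeks in the first two cycles.

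On grade, section 7.6 says "All grade 3 and above adverse events will be entered into OnCore", and section 7.8 says "All grade(s) 3-5 adverse events entered into OnCore® will be reviewed on a monthly basis at the Site Committee meetings".

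**The concern.** The decision concerns pembrolizumab alone, but the look is timed by enrolment. A delayed-arm patient enrolled less than 21 days earlier cannot yet have a pembrolizumab-related event, yet counts towards the six. The same rule can therefore be less sensitive in one of the two randomised arms whose schedules are being compared.

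The wording on grade is a separate gap. Elsewhere the protocol writes grade 3 and above, or grades 3 to 5, when it means that. In section 8.2, two patients with grade 3 events trigger the reduction, but two with events recorded only at grade 4 would not. That can hardly be intended.

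Safety and tolerability are a primary objective, and this is the only numerical arm-level toxicity trigger in the text available. What is at stake is a missed or late arm-level dose reduction. A premature look cannot cause a false trigger.

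**Working it through.** **1. The section's own figures.** The protocol gives no operating characteristics for the six-patient rule. The Simon figures nearby do reproduce. With 10 patients in stage 1, continuation on 2 or more responses, 29 in total and rejection at 6 or more (this final cut-off is inferred), P(reject | p) is the sum over x = 2 to 10 of P(Bin(10,p) = x) × P(Bin(19,p) ≥ 6 − x). This gives 0.0471 at p = 0.10 and 0.8051 at p = 0.30, against the stated 0.0471 and 80.5%. They do not depend on the toxicity look.

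**2. Do the other rules close the gap?** Section 5.2 says who is evaluable, not when the look is held. Sections 7.1.2 and 8.3.1 are satisfied by cycle 1 vorinostat, which section 4.1.2 lists as an investigational drug. The replacement footnote concerns vorinostat holds for neutropenia. None is tied to the six-patient look.

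**3. Trigger probability.** With k patients able to show an event, each with probability q:

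P(2 or more) = 1 − (1−q)^k − k·q·(1−q)^(k−1)

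For k = 6 and q = 0.30: 1 − 0.1176 − 0.3025 = 0.580. The event rates are assumptions; the documents give none.

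| k | q = 0.20 | q = 0.30 |
|---|---|---|
| 6 | 0.345 | 0.580 |
| 5 | 0.263 | 0.472 |
| 4 | 0.181 | 0.348 |
| 3 | 0.104 | 0.216 |

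**4. Accrual.** No rate is stated. Two rates can be inferred from the 4-year study duration and 29 patients per arm, assuming even accrual and no stage 1 pause:

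- 48 months less 24 weeks and 30 days for the last patient leaves 41.5 months: 29/41.5 = 0.70 per month, or 43.6 days apart.
- 48 months less 24 months and 30 days leaves 23 months: 29/23 = 1.26 per month (1.3 below), or 24.1 days apart.

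A rate of 2.0 per month (15.2 days apart) is added as a faster case; it is not derived from the documents.

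**5. Patients with a full 21-day pembrolizumab cycle at the sixth enrolment.** Patient i was enrolled (6 − i) × spacing days earlier. An immediate-start arm needs 21 days since enrolment; the delayed arm needs 42. Probabilities are at q = 0.30.

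| Rate per arm per month | Immediate start: k | P | Delayed start: k | P |
|---|---|---|---|---|
| 0.7 | 5 | 47% | 5 | 47% |
| 1.3 | 5 | 47% | 4 | 35% |
| 2.0 | 4 | 35% | 3 | 22% |

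These counts treat patients with part of a cycle as unable to have an event, so each probability is a floor. In the delayed arm, 5, 5 and 4 patients have started pembrolizumab at the three rates. At 1.3 the fifth has only about 3 days on drug (24.1 − 21), so 35% barely changes. At 2.0 the fourth has about 9 days (30.4 − 21), so that arm lies between 22% and 35%.

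**6. Grade wording alone.** With six fully observed patients and an assumed 30% rate of grade 3 or higher, let a share f of affected patients have only grade 4–5 events. Then q = 0.30 × (1 − f), and the 58% falls to 51% (f = 0.1), 44% (f = 0.2) or 37% (f = 0.3). These shares are also assumptions.

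**The case against.** The strongest reply is that little hangs on this rule. Its only action is a cut to 75%. Section 5.1 reports that 2 and 10 mg/kg every three weeks showed no clinically important safety difference in melanoma, with drug-related grade 3–5 and serious events comparable or lower at the higher dose. That evidence is monotherapy and not this combination, but it is the only dose–toxicity comparison supplied. This part stands, and it sets the size of the point.

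Existing safeguards are also substantial. Section 3.1 has pembrolizumab modified under the manufacturer's guidelines, and section 5.1.1 reduces the agent responsible for an event. Sections 5.1.1.1 to 5.1.1.3 hold or stop treatment in individual patients, often a stronger action than a cut to 75%. Section 7.8 provides weekly Site Committee review of adverse events, monthly review of grades 3–5 and data and safety monitoring committee review of serious reactions. Section 3.7.1 allows termination for toxicity. These limit harm, though none supplies the arm-level threshold that section 8.2 was written to give.

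The single-look assumption is unfavourable to the plan. The wording sets only an earliest time and does not bar a later or repeated look. That too stands: the percentages describe what the text permits, not what it requires. On grade, section 7.6.1 records each change of grade within an episode, so an event first recorded at grade 3 could count even on the literal reading. The wording loss therefore applies only to events never recorded at grade 3.

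A reader might infer that grade 4–5 events go unmanaged, or that the rule cannot work in the delayed arm. The documents support neither. Severe events fall under the individual rules and reviews above, and the rule is inoperative only if all six patients enrol within less than 21 days, an accrual pace the documents do not suggest.

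**Conclusion.** The point holds as a minor, inexpensive correction. Section 8.2 permits a pembrolizumab decision on patients who may not have received the drug or been observed on it, and read literally it leaves out grades 4 and 5. No other rule in the available text repairs either gap.

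The size depends on assumed event rates, even accrual and a single look on the day of the sixth enrolment. At a 30% rate the extra loss from the delayed start is nil at 0.7 patients per arm per month and about 12 percentage points at 1.3 (47% to 35%). At the assumed 2.0 it is at most about 13 points if the immediate-start figure is held at 35%. If the look is repeated later, the timing loss can be recovered. Even a repaired rule misses 42% (100 − 58) at a 30% rate; that is a limit of six patients, not of the wording.

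It would be tempting to conclude that the plan has no other arm-level toxicity rule. That cannot be claimed: the text under the Appendix 4 heading Increase in Adverse Event Rates, and a portion between Appendix 2 and the document lists of Appendix 3, were removed from the copy reviewed and could not be checked.

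**What to change.** Reword section 8.2 so that the final decision in each arm rests on six patients who have received pembrolizumab and completed at least one 21-day cycle after the first dose, or had a qualifying event earlier. Patients who stop before their first pembrolizumab dose should not count towards the six. Define the event as grade 3 or higher non-hematologic toxicity clearly related to pembrolizumab. An earlier look may still be held, but should not be the final one. The 21-day window is proposed as a minimum; the documents set none for this look.

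The cost is timing. The final look comes about 3 weeks after the sixth enrolment in immediate-start arms and about 6 weeks after it in the delayed arm, or later if an uncounted patient must be replaced. With no accrual hold, about 1 to 2 more patients enter the delayed arm in those 42 days at 0.7 to 1.3 per month (42/43.6 = 0.96; 42/24.1 = 1.74), and about 3 at 2.0 per month (42/15.2 = 2.76). Individual toxicity rules and ongoing reviews continue meanwhile. The efficacy alpha and power are unaffected.

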8.3 Analyses Plans

8.3.1 Analysis Populations

We will conduct an intention-to-treat analysis of efficacy. All patients who were randomized will be evaluated.

For evaluation of safety, we will restrict the arm-specific samples to all patients who have received at least one dose of investigational therapy.

8.3.2 Evaluation of Efficacy

For each arm objective response rate (ORR) will be defined as the proportion of participants randomized to that arm whose status is SD or better (CR, PR) at 24 weeks' follow-up. In addition to calculating the ORR, we will calculate the corresponding Agresti-Coull interval 95% confidence interval (CI) (Ref: *Agresti, Alan; Coull, Brent A. (1998). "Approximate is better than 'exact' for interval estimation of binomial proportions". The American Statistician 52: 119–126. doi:10.2307/2685469*). If the lower bound of the 95% CI exceeds 10%, we will reject the null

hypothesis that the regimen is ineffective and conclude that it is sufficiently effective to warrant further study.

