3.1 Characteristics

We propose a three arm, 20-87 patient trial in patients with hormone therapy resistant breast cancer to test the optimal sequence and dosing of epigenetic immune priming in hormone therapy resistant breast cancer. The two arms all include vorinostat, TAM and pembrolizumab to evaluate either sequential priming (Arm A) or, concurrent priming with maximal dosing of both epigenetic and immune modulators in ER+ (Arm B) and ER- (Arm C?) disease. Stage 1 of the trial will evaluate 20 patients, 10 in each arm and randomly assigned. If the response rates are adequate, the trial will proceed to Stage 2 in order to evaluate 58 patients, 29 in each arm.

Given the absence of responses in PD-L1 low patients to pembrolizumab, we will determine the benefits for vorinostat in reversing therapy resistance to pembrolizumab in ER-negative breast cancers (HER2-positive or negative)

Patients will be evaluated for response at 12 weeks by RECIST1.1 (using IR-RECIST) and will continue on therapy if they have stable disease or response at the time of disease evaluations. Patients with progression on imaging, but are clinically stable, may stay on study but will require follow up staging after 4-6 weeks. Patients will be assessed continually for safety and tolerability as well as for any adverse events. If progression on therapy with pembrolizumab, patient may continue if clinical indicated and be re-evaluated after 4-8 weeks.

We will follow AEs of clinical interest as defined by Merck and will dose modify pembrolizumab as per Merck guidelines. We have significant prior experience with vorinostat as an agent and are familiar with managing drug toxicities. In addition, we are experienced with immune-related toxicities as well.

Tissue biopsies of all patients will be collected prior to enrollment to assess for pre-treatment TIL and PD-L-1 expression. A limited number of patients with disease unamenable to biopsy will be allowed to enroll in the trial with prior approval from study PI. Follow up biopsies and peripheral blood collection will be taken from all patients post-treatment, prior to starting cycle 4, to characterize changes in local tissue effects and antigen-specific cellular and humoral immune responses in peripheral blood.

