3.4 Duration of Therapy

In the absence of treatment delays due to adverse events, treatment may continue for 24 months or until:

- Clearly documented disease progression
- Inter-current illness that prevents further administration of treatment
- Unacceptable adverse event(s)
- Patients decides to withdraw from the study
- Significant patient non-compliance with protocol
- General or specific changes in the patients' condition render the patient unacceptable for further treatment in the judgment of the investigator.
- Patients may receive palliative radiation therapy for isolated symptomatic lesions

A subject must be discontinued from the trial for any of the following reasons:

- The subject or legal representative (such as a parent or legal guardian) withdraws consent.
- Confirmed radiographic disease progression

Note: For unconfirmed radiographic disease progression, but clear clinical progression in the opinion of the treating physician or investigator, the patient should be withdrawn from study for progression.

Note: A subject may be granted an exception to continue on treatment with confirmed radiographic progression if clinically stable or clinically improving by symptoms or tumor markers.

Unacceptable adverse experiences as described in Section 7.4

- Intercurrent illness that prevents further administration of treatment
- Investigator's decision to withdraw the subject
- The subject has a confirmed positive serum pregnancy test

- Noncompliance with trial treatment or procedure requirements
- The subject is lost to follow-up

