6.1 Treatment Duration

Eligible patients will receive treatment as described above, in consecutive 3-week cycles, until progression of disease or unacceptable toxicity. Patients are expected to receive treatment for at least 3 cycles, at which time the first evaluation for efficacy will occur. If there is continued safety and tolerability, treatment may continue.

For Arm A: After the initial treatment with vorinostat and tamoxifen, regardless of response of the staging studies, PD-1 will be added to all patients.

For Arm B: patients may remain on study if there is radiological progression however the clinical presentation shows improvement or benefit.

All patients will be restaged during week 9 and 18 via imaging scans, staging will then be continued every 3 cycles until 6 months. After 6 months staging may be spaced out to 6 cycles if clinically indicated.

Patients will be followed for evaluation of safety for at least 30 days after the last dose of study drug. Any study drug-related serious adverse events will be followed until resolution, return to baseline grade, or deemed irreversible by the Investigator.

Subjects who experience a recurrence of the same severe or life-threatening event at the same grade or greater with re-challenge of pembrolizumab should be discontinued from trial treatment.

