6.2 Schedule of Procedures and Observations

The study-specific assessments are detailed in this section and outlined in [Section 6 Schedule of Study Procedures and Assessments](#). Screening assessments must be performed within 28 days prior to the first dose of investigational product. Any results falling outside of the reference ranges may be repeated at the discretion of the investigator. All on-study visit procedures are allowed a window of ± 5 days unless otherwise noted. Treatment or visit delays for public holidays or weather conditions, or patient's personal reasons that do not compromise safety do not constitute a protocol violation. Treatment delays may not exceed 3 weeks, unless discussed with the study team for patients with documented benefit. Patients with proven systemic benefit, who have localized progression in the sanctuary site, may receive localized treatment to that site, including but not limited to radiation therapy, gamma knife or surgery.

A written, signed, informed consent form (ICF) and a Health Insurance Portability and Accountability Act (HIPAA) authorization must be obtained before any study-specific assessments are initiated. A copy of the signed ICF will be given to the subject and a copy will be filed in the medical record. The original will be kept on file with the study records.

All patients who are consented will be registered in OnCore®, the UCSF Helen Diller Family Comprehensive Cancer Center Clinical Trial Management System (CTMS). The system is password protected and meets HIPAA requirements.

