The duration of overall response is measured from the time measurement criteria are met for CR or PR (whichever is first recorded) until the first date that recurrent or progressive disease is objectively documented (taking as reference for progressive disease the smallest measurements recorded since the treatment started).

The duration of overall CR is measured from the time measurement criteria are first met for CR until the first date that recurrent disease is objectively documented.

Duration of stable disease

Stable disease is measured from the start of the treatment until the criteria for progression are met, taking as reference the smallest measurements recorded since the treatment started.

Progression-Free Survival

Progression-free survival (PFS) is defined as the duration of time from start of treatment to time of progression.

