8.0 Statistical Considerations and Evaluation of Results

This trial will determine whether epigenetic priming may enhance the effects of PD-1 inhibitors in patients with ER+ metastatic breast cancer who have progressed on prior hormone therapy and chemotherapy. The trial will contain three arms. Within each arm we will determine whether epigenetic priming will required prolonged pre-exposure to epigenetic modulators or concomitant administration.

Three arms will be tested, with each independent assessment. Patients will be stratified by prior number of hormonal therapy and chemotherapy, then randomized across arms by [name], UCSF.

8.1 Response rates to chemotherapy in breast cancer are less than 20%. Historical response rates to pembrolizumab and MPDL3280A have been 18% and 19%, respectively, in patients whose tumors are PD-L1 positive. Hence, we expect the response rate for unselected patients and patients with no PD-L1 expression would be 10% or less. In contrast, we anticipate that vorinostat will increase the response rate to 30%**Sample Size and Power Estimate**

Response rates to hormonal therapy and MTOR or HDAC inhibitors have been reported as 5-20% (19% for VOR-Tam, 6% for entinostat-exemestane, 12% for exemestane-everolimus). Given the recent additions to hormonal therapy this trial will treat a patient population that has received more lines of therapy than these trials, however we are interested in an ORR of >30%.

8.2 For each arm: Using an Optimal Simon's two-stage design (Simon, 1989), the null hypothesis (H₀) that the true response rate is 10% will be tested against a one-sided alternative. In the first stage, 10 patients will be accrued and a decision will be made to continue or stop accrual based on the observed objective response rate (ORR). If there are 0 or 1 objective responses at 24 weeks in these 10 patients, accrual to this arm of the study will be stopped. Otherwise, 19 additional patients will be accrued for a total of n=29. We estimate that each regimen under evaluation will achieve ORR ≥ 30%. This study is designed to have an alpha of 0.0471, and a power of 80.5% to test the null hypothesis H₀: ORR = 10% against an alternative hypothesis, H_A: ORR = 30%, where ORR is defined as CR, PR, or SD ≥ 24 weeks where arms are enrolled independently.**Interim Analyses**

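### The primary endpoint has two definitions that disagree on a patient who progresses before week 24 and later reads as stable disease

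*Combined protocol and SAP*

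**What the plan says.** The endpoint is stated twice in the statistical part of the protocol.

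- Section 8.3.2, the analysis rule, counts randomised patients "whose status is SD or better (CR, PR) at 24 weeks' follow-up". This is status at one time point.
- Section 8.0, in the sample-size paragraph numbered 8.2, says "where ORR is defined as CR, PR, or SD ≥ 24 weeks". Section 7.3 explains how long stable disease lasts: "Stable disease is measured from the start of the treatment until the criteria for progression are met".

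Three sections allow patients to continue after radiographic progression. Section 3.1 does so for clinically stable patients, with repeat staging. Section 3.4 goes further: "A subject may be granted an exception to continue on treatment with confirmed radiographic progression if clinically stable". Section 6.1 says, under Arm B, that "patients may remain on study if there is radiological progression however the clinical presentation shows improvement or benefit".

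On criteria, the synopsis (efficacy assessments) assigns the primary endpoint to RECIST 1.1, and the secondary objectives list irRC as an additional calculation. Section 3.1, however, reads "Patients will be evaluated for response at 12 weeks by RECIST1.1 (using IR-RECIST", closing the parenthesis there. Section 7.1.1 applies RECIST together with irRC and does not say which decides the primary endpoint.

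Restaging in Table 6 (footnote e) falls at weeks 9 and 18, then after cycle 9, which is 9 × 3 = week 27. No scan is scheduled at week 24.

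**The concern.** Status at a date and stable disease lasting to that date are different endpoints as soon as patients are followed and scanned after progression, and this protocol allows that. Under the first, a patient who progressed and then shrank somewhat is a success. Under the second, the same patient failed on the day of progression. Immune criteria differ from RECIST chiefly in how they treat early apparent progression, so the unclear reference to IR-RECIST bears on the same patients.

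The endpoint drives both the stage 1 stop (0 or 1 success in 10) and the final decision on 29 patients. With counts this small, the classification of one or two patients can decide an arm. The trial is open label, so the rule should be fixed before outcomes are seen.

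**Working it through.** **1. The plan's own figures.** Section 8.0: "This study is designed to have an alpha of 0.0471, and a power of 80.5" percent, null rate 10%, alternative 30%, 10 patients in stage 1 (stop at 0 or 1), 29 in total. The final cut-off is not stated. With success meaning at least c of 29,

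P(success | p) = Σ over x = 2…10 of Bin(x; 10, p) × P[Bin(19, p) ≥ c − x].

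For c = 6 this gives 0.0471 at p = 0.10 and 0.8051 at p = 0.30, so the stated design is reproduced with c = 6.

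**2. The cut-off that 8.3.2 implies.** It requires the Agresti-Coull 95% lower bound to exceed 10%. With ñ = 29 + 1.96² = 32.84 and p̃ = (x + 1.92)/32.84, the bound is p̃ − 1.96 √[p̃(1 − p̃)/ñ].

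- x = 6: 0.2412 − 0.1463 = 0.095, not above 10%.
- x = 7: 0.2716 − 0.1521 = 0.120, above 10%.

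So 8.3.2 needs 7 of 29. Both cut-offs are carried below.

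**3. One patient under both definitions** (target-lesion rules in 7.3, no new lesion, non-target disease not progressing). Baseline sum 50 mm.

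- Week 9: 61 mm. (61 − 50)/50 = +22%, and 11 mm exceeds the 5 mm minimum: progression.
- The patient is clinically stable and continues. Later scan: 55 mm. (55 − 50)/50 = +10% over the nadir, below the 20% threshold. Partial response would need 35 mm or less. That scan reads as stable disease.
- If that scan supplies the 24-week status, 8.3.2 taken literally gives a success.
- Under 8.0 with the duration rule in 7.3, stable disease ended at week 9, so the patient is a failure.

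The definitions can also disagree the other way. In 8.0 the 24-week condition is attached only to stable disease. A partial response at week 9 followed by progression at week 18 could count there, but not under 8.3.2 if the patient is still progressed at week 24.

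**4. Sensitivity of the decision.** The documents give no frequency for such patients. As an assumption, let the true rate be 10% and add d percentage points of patients counted only because earlier progression is ignored. Then p = 0.10 + d in the formula of step 1. The stage 1 stop probability is P[Bin(10, p) ≤ 1].

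| d (points) | expected extra per 29 | success, 7/29 | success, 6/29 | stage 1 stop |
|---|---|---|---|---|
| 0 | 0 | 1.8% | 4.7% | 73.6% |
| 1 | 0.3 | 2.8% | 6.9% | 69.7% |
| 2 | 0.6 | 4.3% | 9.5% | 65.8% |
| 4 | 1.2 | 8.4% | 16.2% | 58.2% |
| 9 | 2.6 | 26.1% | 38.4% | 40.7% |

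Under the 7/29 rule the error is 0.0459 at p = 0.122 and 0.0477 at p = 0.123, so it stays within the stated 0.0471 until a little over 2 points are added. Under the 6/29 rule any addition takes it above 0.0471.

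**5. Stage 1.** One reclassified patient turns 1 of 10 (stop) into 2 of 10 (continue).

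**The case against.** The strongest reply is that the rest of the protocol already answers the question. The synopsis assigns the primary endpoint to RECIST 1.1, irRC is secondary, Section 7.3 closes both best overall response and stable disease at progression, and 8.0 asks for at least 24 weeks of stability. Permission to stay on study concerns treatment and does not say that a patient is scored a success. The planned 24-week landmark PFS would also expose any progressor counted in the primary rate. Much of this stands: a careful analyst would probably exclude these patients. But 8.3.2 uses neither best overall response nor duration of stable disease and refers to neither, and landmark PFS decides neither stage 1 nor the final conclusion.

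Three stronger readings are tempting and not supported.

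- *That local treatment of a progressing brain lesion restores success.* Section 6.2 does say that patients with systemic benefit "who have localized progression in the sanctuary site, may receive localized treatment to that site". But if the lesion is new, Table 7 gives progression whatever the other lesions do. Section 6.3.3 also restricts radiation to a consultation exception and otherwise has patients who need it removed. Only growth of a pre-existing lesion could behave like the example in step 3.
- *That the comparison of schedules is biased because 6.1 writes its permission under Arm B.* Sections 3.1 and 3.4 are not arm-specific, 6.1 does not exclude the other arms, and 3.6 and 8.0 assess each arm independently. No between-arm primary test is planned.
- *That the error rate is in fact 8% to 26%.* Those values belong to an assumed 4 to 9 points, which has no source in the documents. With up to 2 points the 7/29 rule stays within the stated alpha.

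**Conclusion.** The inconsistency is real and lies in the primary endpoint. Section 8.3.2 read literally and Section 8.0 read with 7.3 classify the same patient differently, and the protocol's own continuation provisions make such patients possible. It is an undefined rule, not an instruction to count progressors as successes.

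The size cannot be determined from the documents. It depends on how many patients progress, continue, fall back below 20% over the nadir without a new lesion, and are then scored on the later scan alone. The table in step 4 shows what various numbers would do and is not an estimate. What holds without that assumption is that the margins are one or two patients: 1 against 2 of 10 at stage 1, and 6 or 7 of 29 at the end. The stated alpha and power hold for whichever definition is adopted only if the 10% and 30% rates refer to that same definition.

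**What to change.** Put one definition in both the sample-size paragraph (8.2) and 8.3.2: complete response, partial response or stable disease by RECIST 1.1 at the 24-week assessment, with no RECIST 1.1 progression at any assessment up to then, whether or not treatment continues. Name the scheduled scan that serves as the 24-week assessment, since the calendar has weeks 9, 18 and about 27.

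State that RECIST 1.1 governs the primary endpoint, delete the IR-RECIST parenthesis from 3.1 for that endpoint, and report irRC separately as the planned secondary analysis.

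Reconcile Sections 3.1, 3.4 and 6.1 on staying on study after progression. No change to the care of these patients is proposed.

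The cost is wording. Sample size and stage 1 rule are unchanged, and the scans are already collected. The primary rate may come out slightly lower, and patients whose benefit appears only after early progression will be seen only in the irRC analysis. The change should be made before any arm's stage 1 decision.
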